eCRF Electronic Case Report Form

EU European Union

FDA Food and Drug Administration

FPI First Patient In
GH Growth hormone
GP General Practitioner

HV SDS Height velocity standard deviation score

IGF-1 Insulin-like growth factor-1

LPI Last Patient In
LPO Last Patient Out

NCR Paper Non carbon copy paper
OGTT Oral glucose tolerance test
PAC Post-approval commitment
PMC Patient Management Centre

PP Per Protocol

r-hGH Recombinant human growth hormone

SAE Serious Adverse Event

SALTO SAizen® Long Term Observational study

SD Standard deviation

SDS Standard deviation score SGA Small for gestational age

SUSAR Suspected Unexpected Serious Adverse Reaction

ULN Upper Limit of Normal

List of Figures	•	
Figure 1	Study Design	20
Figure 2	Determination of planned sample size	34
List of Tables		
Table 1	Summary of Data to be Collected*	26
Table 2	Subject Identifier (examples)	39

1 Synopsis

Study title	Prospective and retrospective, single-cohort, multicentre observational long-term study in short children born small for gestational age (SGA) after treatment with Saizen® or with other recombinant human growth hormone (r-hGH) products		
Short Title	SAizen® Long Term Observational study (SALTO)		
Study number	EMR 200098_008		
EudraCT number	Not applicable		
EU PAS number	EUPAS16520		
Sponsor	Merck KGaA, Darmstadt, Germany		
Phase	Phase IV		
Study under IND	☐ yes ⊠ no		
FDA "covered study"	☐ yes ⊠ no		
Study center(s)/country(ies)	Approximately 40 to 60 centres globally		
Planned study period (first enrolment-last subject out)	First subject enrolled after cessation of Saizen® treatment in 2011; expected last subject in by 2020 and last subject out by 2030.		
Study objectives	Primary objective of the study:		
	• To assess the long-term safety of Saizen® or other r-hGH treatment for 10 years after cessation of treatment, in terms of occurrence of type 2 diabetes mellitus and malignancies, in a minimum of 200 subjects born SGA who received Saizen® or other r-hGH products for the treatment of short stature		
	Secondary objectives of the study:		
	To assess occurrence of metabolic syndrome		
	To assess glucose metabolism parameters		
	To characterize the observed malignancies		
	To correlate the occurrence of metabolic syndrome and/or glucose metabolism disorders or malignancy to familial inheritance		
	To correlate the occurrence of metabolic syndrome and glucose metabolism disorders or malignancy to subject characteristics and medical history.		

Study design and plan	Prospective and retrospective, single-cohort, multicentre, multinational observational long-term follow-up study in subjects born SGA who received Saizen® or other r-hGH products for the treatment of short stature.		
	The study will comprise a 10-year safety follow-up period after cessation of r-hGH treatment in short children born SGA who had received Saizen® or other r-hGH products in the frame of a sponsored clinical study or in the post-marketing setting.		
	The subjects may be enrolled up to 5 years after treatment cessation.		
Planned number of subjects	We aim to enrol approximately 300 subjects in the study in order to have a target of 200 subjects completing the study		
Schedule of visits and assessments	Following cessation of r-hGH therapy, subjects will be enrolled in the study after signing an informed consent form.		
	No specific medical visits are scheduled for study subjects because of the observational nature of the study. Only data available as per the subject's routine medical care will be collected.		
	During the course of the study, subjects are not required to visit the study Investigator. Subjects may go to their general practitioner (GP) or other treating physician for their routine medical visits. Therefore, the medical data of interest (when/if available) will be collected by the investigator from the patient's treating physician/GP.		
	In addition, the investigator will contact the subjects 5 and 10 years after discontinuation of r-hGH therapy in order to obtain information on any change in medical condition.		
	The clinical research organization's (CRO) dedicated patient management centre (PMC) will contact the subject at least once a year to update and confirm subjects' and treating physicians' contact information, and to identify any change in health status/medical history.		
Diagnosis and main inclusion and exclusion criteria	 Inclusion criteria Eligible subjects (are): Male and female subjects who were born SGA Have received r-hGH therapy for the treatment of short stature due to SGA Have permanently discontinued r-hGH treatment within 5 years prior to study enrolment Parents or guardians and/or subjects have given written 		
	informed consent.		

	 Exclusion criteria Patients unwilling and/or parents/guardians who are not capable of ensuring compliance with the study protocol. Patients enrolled in an interventional trial Patients enrolled in an observational trial of a similar nature to the SALTO study, where the protocol includes reporting of incidence of type 2 diabetes mellitus and/or malignancies after cessation of r-hGH therapy. 		
Investigational Medicinal Product (s): dose/mode of administration/dosing schedule	Not Applicable (observational study).		
Reference therapy(ies): dose/mode of administration/ dosing schedule	None (post-treatment observational study).		
Planned treatment duration per subject	None (post-treatment observational study).		
Primary endpoint(s)	Incidence of type 2 diabetes mellitus		
	Incidence of any malignancy		
Secondary endpoint(s)	• Incidence of metabolic syndrome and changes in glucose metabolism parameters (glycaemia parameters – fasting plasma glucose and postprandial glucose, fasting plasma insulin levels, HbA1c, 2-hour oral glucose tolerance test (OGTT) results, blood pressure, lipid parameters).		
	 Parameters related to malignancies (typology, size and location as applicable, grading, severity, treatment, outcome) 		
	Correlation of type 2 diabetes mellitus and/or malignancy will be established against blood pressure, body mass index, lipid parameters, medical history and familial inheritance		
Statistical methods (includes sample size calculation)	It has been agreed with the Health Authorities to organize an observational study to follow-up 200 short children born SGA for 10 years after cessation of treatment with Saizen® or other r-hGH products. In order to compensate for an estimated 35% loss to follow-up, we will recruit 150% of the requested target number of 200 subjects. Hence, a sample size of approximately 300 subjects is targeted for study enrolment.		

Numbers and proportions of subjects having the events (type 2 diabetes mellitus and any malignancy), will be computed, as will the incidence rate per subject-years of follow-up during the 10-year follow-up. Analysis of correlations of the primary endpoints with subject characteristics (e.g., age, blood pressure, Body Mass Index [BMI], family history) and possible confounding factors of the diseases (e.g., concomitant treatment, environmental factors) will be conducted. Exploratory analysis will be performed for each brand of r-hGH product if permitted by sample size per brand.

2 Sponsor, Investigators and Study Administrative Structure

The Sponsor of this study is Merck KGaA, Darmstadt, Germany.

The Coordinating Investigator of this study is PPD

Data collection, management and analysis will be performed by the Contract Research Organisation (CRO) PPD , on behalf of the study Sponsor. The CRO will have a dedicated patient management centre (PMC) to directly contact subjects either by email, letter or phone.

will be responsible for the clinical trial documents to be submitted to regulatory authorities, the conduct of the clinical trial, data management, statistical analysis, as well as clinical trial and safety reporting. Further details will be provided in a separate document and updated as necessary. Clinical quality assurance will be performed under the responsibility of the Development Quality Assurance department at Merck KGaA Darmstadt, Germany.

Investigators (i.e., paediatricians and/or endocrinologists) of this study are the ones who treat short children born SGA with Saizen® or other r-hGH products at their clinics and will be responsible for screening and enrolling eligible subjects in this study (see section 9.1).

Subjects who will be enrolled in the study are those who have permanently terminated/discontinued r-hGH therapy for the treatment of growth disturbance in short children born SGA, and who might have been enrolled in previous sponsored clinical studies in the SGA indication or may come from a post-marketing setting. During the course of the study, subjects are not required to visit the study Investigator. Therefore, to ensure adequate collection of the post-treatment data, Investigators will obtain medical information through the subject's treating physician/GP.

3 Background Information

Treatment with Saizen® for short children born small for gestational age (SGA) was approved in Europe in 2005. During the approval process, the company was requested by the Health Authorities to conduct a study in about 200 subjects born SGA after the cessation of their treatment with Saizen® and to focus on the risk of developing type 2 diabetes mellitus and malignancies. Therefore, the company has agreed with the Italian Health Authorities (Italy being the Reference Member State of the registration procedure of Saizen® in Europe) to fulfil this request as a Post-Approval Commitment.

Saizen®, recombinant human growth hormone (r-hGH), was initially registered in 1988 for the long-term treatment of children with growth failure due to inadequate secretion of endogenous growth hormone (GH). The following indications have been registered as further steps: Growth failure in girls due to gonadal dysgenesis (Turner Syndrome), Growth failure in pre-pubertal children due to chronic renal failure and GH deficiency in adults. These indications were extended in April 2005 to the treatment of short children born SGA without signs of catch-up growth (3).

The diagnosis of SGA is based on anthropometric parameters at birth and thus requires: 1) accurate knowledge of the gestational age, 2) accurate measurements of weight, length, and head circumference at birth and 3) a cut-off against reference data from the relevant population (< -2 standard deviation score [SDS] from the mean of weight and/or length). Babies born SGA represent a significant proportion of subjects with short stature as adults (4). Approximately 10% of children born SGA fail to catch up with regard to growth during childhood and remain short, with a height below -2SDS (5).

It has been hypothesized that the persistence of short stature in SGA subjects may be the manifestation of a GH or an IGF-1 resistance. In point of fact, the majority of SGA subjects have normal values of GH secretion and only some show evidence of GH deficiency. More inclusive of SGA subjects at large, serum levels of IGF-1 and to some extent IGF-BP3 are found to be significantly decreased (< -1 SD from mean levels) but with a wide range of levels indicating possible heterogeneity in the mechanism of growth failure from insufficient IGF-1 to IGF-1 insensitivity (4). This is the basis of the Barker hypothesis, which suggests that an *in utero* imprinting occurs leading to resistance to multiple hormones; thus, even if SGA growth failures are due to causes other than GH deficiency, these children can be considered as having manifestations of a GH and/or IGF-1 resistance status (6).

The use of GH in SGA has been explored for nearly 40 years. Early intervention with GH for those with severe growth retardation is warranted. In current practice, SGA children over the age of 4 years can be considered for GH treatment when their current height is < -2.5 SDS and when they have failed to show catch-up growth (HV SDS < 0 during the last year) (7),(8). Average height gains after 3 years of GH treatment range from 1.2 to 2.0 SD for doses of 35 to 70 μg/kg/d (4). The recommended daily dose according to product labelling is 0.035 mg/kg body weight (or 1 mg/m² per day, equal to 0.1 IU/kg/day or 3 IU/m²/day) every day, by subcutaneous administration.

Further effects of long-term GH treatment include beneficial effects on body composition, carbohydrate metabolism, blood pressure and lipids in short children born SGA (9). A consistent positive dose-effect relationship on catch-up growth has also been demonstrated with Saizen® (10).

Children born SGA can show some degree of insulin resistance (4). GH treatment has been acknowledged to induce insulin resistance (11) and it was thus recommended that the treatment of children with recombinant GH should be submitted to long-term follow-up. Large international databases have been designed to have some degree of extended monitoring (12). Within the context of the approval of Saizen® in short children born SGA, the long-term follow-up study will focus on:

1. **Type 2 diabetes mellitus and metabolic syndrome risk**: low birth weight might increase risk of type 2 diabetes and metabolic syndrome in adulthood (5). GH has been associated with increased insulin levels and insulin resistance (13), (14). It is currently unknown whether GH therapy for SGA is associated with benefits or amplification of metabolic consequences in adulthood (4). Therefore, long-term follow-up is recommended (4). A recent study in a small population shows that at 6.5 years after discontinuation of GH treatment, risk factors for type 2 diabetes and metabolic syndrome were comparable in treated and untreated young SGA adults, with increased fasting glucose and higher fasting insulin levels during treatment recovering after discontinuation (5),(19).

2. Malignancy risk: low birth weight has not been shown to be associated with increased risk of cancer in general, with the possible exceptions of testicular and renal cancer (4). A number of studies were retrieved in the published literature discussing the occurrence and/or recurrence of cancer or neoplasm during GH therapy. In one medium-sized and two large studies, GH therapy was not associated with an increase in the incidence of a first cancer compared to the general population.

However, GH treatment during childhood of survivors of cancer treatment has also been shown to increase slightly the relative risk of a second neoplasm (15), (16). Growth hormone therapy studied in two populations of cancer survivors, one with a control group, found an elevated risk of developing a secondary solid tumour in childhood cancer survivors treated with GH compared with non-treated survivors for one and a statistically significant raised frequency of colon cancer mortality after pituitary-derived GH treatment in another.

This observation is however disputed, given that other surveillance studies revealed no increase in observed cancer risk (17). The above results are based on a very small number of cases and may therefore require cautious interpretation.

There have been rare reports of brain tumours (de novo/recurrence) or leukaemia and extra-cranial solid tumour in subjects treated with Saizen® in the post-marketing surveillance period. From the currently available data, there is no evidence suggesting that Saizen® may increase the risk of cancers in treated subjects. It must also be noted that with an overall increase in subject-years of exposure, adverse events (AEs) which are related to commonly experienced medical conditions (as seen in the general population) tend to also be reported in the population treated with GH. However, no increase of reporting rates concerning neoplasms, both de novo and recurrence, was identified cumulatively since first marketing authorization of Saizen®.

4 Study Objectives

Primary objective of the study:

To assess the long-term safety of Saizen® or other r-hGH treatment for 10 years after cessation
of treatment, in terms of occurrence of type 2 diabetes mellitus and malignancies, in a minimum
of 200 subjects born SGA who received Saizen® or other r-hGH products for the treatment of
short stature

Secondary objectives of the study:

- To assess occurrence of metabolic syndrome
- To assess glucose metabolism parameters
- To characterize the observed malignancies
- To correlate the occurrence of metabolic syndrome and/or glucose metabolism disorders or malignancy to familial inheritance
- To correlate the occurrence of metabolic syndrome and glucose metabolism disorders or malignancy to subject characteristics and medical history.

5 Investigational Plan

5.1 Overall Study Design and Plan

This study is a prospective and retrospective, single-cohort, multicentre, observational long-term post-approval commitment study in subjects born SGA, with no specific age restrictions, who received Saizen® or other r-hGH products for the treatment of short stature. It is a multinational study that will be performed at up to approximately 40 to 60 sites globally. The study will consist of a 10-year post-treatment safety assessment in subjects who were previously treated with r-hGH and who completed or permanently discontinued r-hGH therapy. Eligible subjects may have been enrolled in sponsored clinical studies or may have received r-hGH products in a post-marketing setting. Subjects may be enrolled at any time from the day after their last r-hGH dose up until 5 years after treatment cessation. The maximum duration of follow-up will be 10 years after treatment cessation. All subjects must have received r-hGH products for the treatment of short stature due to SGA as approved per country product label. There is no control group.

The overall objective is to collect safety data with a primary focus on type 2 diabetes mellitus and malignancies during the 10-year follow-up period after termination of r-hGH treatment in the SGA subjects (see section 4).

The aim is to have a final study population of 200 subjects after 10 years of follow-up for analysis. Approximately 300 subjects will be enrolled at study initiation in order to compensate for anticipated loss to follow-up (see section 8.1).

All subjects must sign the Informed Consent Form (ICF) to be enrolled in the study. Subjects may sign the ICF on the day after r-hGH treatment discontinuation (see section 9.2) and up to 5 years after treatment cessation. Prior to enrolment into the study, subjects who are currently being treated with an r-hGH product may be asked to optionally sign a Contact Information Consent Form (CICF) in order to allow the CRO's PMC to contact the subjects and track subject contact information only (see section 9.2).

Because SALTO is a post-treatment observational study, no scheduled study-specific visits, assessments or interventions are scheduled during the study (see section 7.1).

[figure not shown]
However, clinical data will be collected by the Investigator on an ongoing basis and when available during the course of this study through the subject's treating physician/GP or when provided directly by the subject/person of contact (see sections 7.1; 9.1; 9.2; 10.1). Additionally, the investigator will contact the subjects at roughly 5 and 10 years after discontinuation of r-hGH treatment in order to obtain any additional available relevant medical information (see section 7.1).

In order to minimize the subject loss during the 10 years of the follow-up study, the CRO's dedicated PMC will contact the subjects once a year to update/confirm subjects' and treating physicians' contact information in order to send them the "Yearly Subject and Investigator SALTO kits", and to identify any change in health status/medical history. If any relevant change is identified by the PMC, the PMC will notify the investigator, who will gather the relevant information from the treating physician/GP (see section 7.1).

The 5-year interim data and 10-year post-treatment data will be analysed (see section 8.6). If possible, correlation of type 2 diabetes mellitus and/or malignancy will be assessed against blood pressure, body mass index, lipid parameters, medical history and familial inheritance studies (see section 8.5).

Thus, it is anticipated that most subjects will participate in the present study between 2020 and 2030 (see Figure 1). First patient in in 2011, last patient in by 2020, and last patient out by end of 2030.

Figure 1 Study Design

5.2 Discussion of Study Design

The principal clinical concerns relating to treatment of children born SGA who are treated with GH are the potential for development of metabolic abnormalities associated with insulin resistance (metabolic syndrome or type 2 diabetes mellitus) and the potential for the development of malignancy, as described above. These potential concerns are reflected in the choice of primary and secondary endpoints.

5.2.1 Inclusion of Special Populations

Not applicable.

5.3 Selection of Study Population

The subject population for this study will be any subject born SGA that was treated with Saizen® or other r-hGH products for short stature, and who has permanently ended r-hGH treatment within 5 years prior to enrolment in this study.

5.3.1 Inclusion Criteria

For inclusion in the study, all of the following inclusion criteria must be fulfilled:

Eligible subjects (are):

- Male and female subjects who were born SGA
- Have received r-hGH therapy for the treatment of short stature due to SGA
- Have permanently discontinued r-hGH treatment within 5 years prior to study enrolment
- Parents or guardians and/or subjects have given written informed consent.

5.3.2 Exclusion Criteria

Subjects are not eligible for this study if they fulfil any of the following exclusion criteria:

- Patients unwilling and/or parents/guardians who are not capable of ensuring compliance with the study protocol.
- Patients enrolled in an interventional trial
- Patients enrolled in an observational trial of a similar nature to the SALTO study, where the
 protocol includes reporting of incidence of type 2 diabetes mellitus and/or malignancies after
 cessation of r-hGH therapy

5.3.3 Criteria for Randomization or Initiation of Treatment with the Investigational Medicinal Product

Not applicable – this is a post-treatment observational study.

5.3.4 Criteria for Subject Withdrawal

5.3.4.1 Withdrawal from the Study

Subjects will be informed that they have the right to withdraw from the study at any time, without prejudice to their medical care, and they are not obliged to state their reasons.

Withdrawal will be mandatory if the subject is reported to have started an r-hGH therapy during the course of the study.

Subjects who have withdrawn will not be replaced, and the reason for withdrawal will be collected.

5.3.4.2 Withdrawal from the Investigational Medicinal Product

Not applicable – post-treatment observational study.

5.3.5 Premature Discontinuation of the Study

The whole study may be terminated or suspended upon request of Competent Authorities.

5.3.6 Definition of End of Study

The study will end once the last enrolled subject has completed the study (i.e., early termination or 10 years of follow-up after cessation of treatment).

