7.4.1.3 Definition of the Adverse Event Reporting Period

The AE reporting period for safety surveillance is defined as the 10-year period after cessation of r-hGH treatment (i.e., during the 10 years after the date of last r-hGH administration).

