8.1 Sample Size

It has been agreed with the Health Authorities to organize an observational study to have followup data on a minimum of 200 subjects born SGA for 10 years after cessation of Saizen® or other r-hGH therapies.

It has been estimated that up to 35% of subjects are likely to be lost or will drop out during the 10-year study duration (which can be due to withdrawal of consent, lost to follow-up, or death). Therefore, it was decided to recruit approximately 300 subjects in the SALTO study to have the 200 subjects for the final analysis at 10 years of follow-up. The sample size of 300 subjects represents 150% of the 200 subjects completing the study, as requested by the Health Authorities.

While recruitment is still open, the Sponsor will closely monitor the subject dropout rate to determine the need to recruit additional subjects. If the attrition rate is anticipated to be greater than 35%, additional subjects may be recruited to maximize the probability that 200 patients will have completed the study.

Figure 2 Determination of planned sample size.

^{*}Discontinuation includes: Lost to FU, protocol deviation, non-compliance, AEs, patient decision and other reasons.

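### Section 5.3.6 ends the study when the last enrolled subject finishes, but follow-up runs from the last r-hGH dose, so read literally it can stop the study before other subjects reach year 10

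*Protocol*

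**What the plan says.** The only definition of the end of the study is in protocol section 5.3.6: "The study will end once the last enrolled subject has completed the study". A parenthesis then explains completion as either terminating early or reaching year 10 after treatment stopped.

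Follow-up is counted from the last dose, not from enrolment:

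- Section 5.1: "The maximum duration of follow-up will be 10 years after treatment cessation".
- Section 7.4.1.3 sets the adverse event reporting period as "during the 10 years after the date of last r-hGH administration".
- Section 7.1 has the investigator call each subject 5 and 10 years after r-hGH was stopped.

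Entry is spread over a wide window. Section 5.1: "Subjects may be enrolled at any time from the day after their last r-hGH dose up until 5 years after treatment cessation".

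The calendar in section 5.1 is "First patient in in 2011, last patient in by 2020, and last patient out by end of 2030". Section 8.1 plans about 300 subjects, allowing for up to 35% loss, "to have the 200 subjects for the final analysis at 10 years of follow-up".

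**The concern.** Tying the end of a study to the last person enrolled is safe when everyone's follow-up starts at enrolment and has the same length, because order of entry is then order of exit. Neither condition holds here. Measured from enrolment, planned follow-up ranges from 10 years (entry the day after the last dose) down to 5 years (entry 5 years after it). Someone who enrols last with a long gap since the last dose can finish years before someone who enrolled earlier with a short gap.

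The parenthesis in section 5.3.6 adds a second route to the same result, since the last enrolled subject's withdrawal also counts as completion.

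What is at stake is the late follow-up of subjects who stopped r-hGH most recently. They include those enrolled soon after stopping, whose data are mostly prospective. Both primary endpoints, type 2 diabetes mellitus and any malignancy, are counted over the full 10 years, and the commitment to the Health Authorities is for 200 subjects followed that long.

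**Working it through.** **The plan's own figure.** 200 × 1.5 = 300, as section 8.1 says. Dividing by retention gives 200 / (1 − 0.35) = 308, so about 300 is within 3%. Looking forward, 300 × 0.65 = 195, and 300 subjects give exactly 200 completers at 33.3% loss. The sample size is not in dispute. The check shows only that there is little slack.

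**Example in dates.**

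- Subject A enrols in January 2020, the day after the last dose. Year 10 falls in January 2030.
- Subject B is the last to enrol, in December 2020, with a last dose in December 2015. Year 10 falls in December 2025.
- Under section 5.3.6 read literally, the study ends in December 2025. A then has about 5.9 years of follow-up and no year-10 contact.
- If B withdraws one month after enrolling, the study ends in January 2021, when A has about one year.

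**Who is cut off.** Let L be the last enrolled subject's lag (years from last dose to enrolment). If that subject stays in, the study ends at last enrolment + 10 − L. Everyone whose last dose came after last enrolment − L is cut off. For another subject, let a be the time from that subject's enrolment to the last enrolment, and u that subject's own lag. The subject is cut off when a + u < L.

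**Size, main model.** The protocol gives neither the accrual nor the lag pattern, so these are assumptions: 300 subjects, enrolment uniform from mid-2011 to the end of 2020, lag uniform on 0 to 5 years, and 35% loss per 10 years at a constant hazard from enrolment.

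- Hazard: h = −ln(0.65) / 10 = 0.0431 per year.
- Completers if everyone is followed to year 10: 300 × 0.65 × (e^(5h) − 1) / (5h) = 300 × 0.65 × 0.2403 / 0.2154 ≈ 218.
- Simulation under the literal rule, last enrolled subject staying in:

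| Lag of last enrolled subject | Completers lost | Completers left |
|---|---|---|
| 0 years | 0 | about 218 |
| 2.5 years | 13 | about 205 |
| 4 years | 35 | about 183 |
| 5 years | 55 | about 163 |

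- Averaged over the lag, about 199 remain.
- The last enrolled subject drops out in roughly 27% of runs. If that closes the study, about 127 completers remain on average in those runs.
- Combined: 0.73 × 199 + 0.27 × 127 ≈ 180.

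**Sensitivity.** Take 35% loss for every subject whatever the lag, so that 195 completers are expected before any cut-off, and accrual uniform over 9 years. The share cut off is L² / (2 × 9 × 5) = L² / 90:

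- L = 1: 1.1%, and 195 × 0.989 ≈ 193.
- L = 2.5: 6.9%, and 195 × 0.931 ≈ 181.
- L = 5: 27.8%, and 195 × 0.722 ≈ 141.

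If enrolment is concentrated in the last 5 or 3 years, L = 2.5 leaves about 171 or 154. The direction is the same throughout, but the size varies widely.

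**The case against.** The strongest reply is that the sponsor plainly means the last subject to complete. Follow-up is set per subject in sections 5.1 and 7.4.1.3, the year-10 contact is promised to each subject, section 5.3.5 names only the Competent Authorities as able to stop the study early, and the 2030 date leaves room for a subject who stopped in 2020 to reach year 10. The phrase can even be read as the last of the enrolled subjects to complete, with the parenthesis listing the ways in which any subject completes. This stands as evidence of intent. It does not remove the conflict: section 5.3.6 is the only end-of-study definition, its natural reading points to one person identified by order of entry, and nothing says that others continue after that person finishes.

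Three stronger readings are tempting, and the protocol does not support them:

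- A reader might infer that the rule contradicts "last patient in by 2020, and last patient out by end of 2030". It does not. The date is an upper limit, and an end in 2021 or 2025 would respect it. The conflict is with the 10-year reporting period in section 7.4.1.3 and the year-10 contact in section 7.1.
- A reader might infer that completers must fall below 200. They need not. With a lag near 0 and no drop-out of the last enrolled subject, nobody is lost, and with a lag of 2.5 years the main model still leaves about 205. The overall mean of about 180 is pulled down by the runs in which that one subject drops out and the study is assumed to close, which is the least plausible application of the rule. In the sensitivity model the expected count is 195 before section 5.3.6 has any effect, so that part of the shortfall is not due to this sentence.
- A reader might infer that the rule sets the final database lock. Section 9.3 ties lock to completion of quality assurance procedures, and nothing links it to section 5.3.6.

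Section 8.1 allows extra recruitment if loss is expected to exceed 35%, but only while recruitment is open, so it would not repair a cut-off that comes later.

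**Conclusion.** Wrong as written. Section 5.3.6 picks out the wrong subject for a study whose clock starts at the last dose, and taken literally it can end follow-up before other subjects reach year 10. That puts the 200-completer target at risk without making failure certain. Under the main model, about 218 completers become about 218 to 163 if the last enrolled subject stays in (mean about 199), and about 127 on average if that subject's early termination closes the study. These counts rest on assumed accrual, lag and loss patterns and show a range, not a forecast. The defect itself follows from the protocol's text alone. It is probably a drafting slip, but it sits in the operative clause of a study planned to run to 2030.

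**What to change.** Replace the sentence in section 5.3.6 with: *The study will end when every enrolled subject has either reached 10 years after the last r-hGH dose or terminated early.* The end of the study is then the latest of these dates over all enrolled subjects.

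The cost is one sentence in the next amendment. With the last enrolment by 2020, the latest last dose also falls by 2020, so the latest year-10 date falls by the end of 2030, as already planned. No subjects, visits or time are added.
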